7.0 Data and Specimen Banking*

7.1 *If data or specimens will be banked for future use, describe where the specimens will be stored, how long they will be stored, how the specimens will be accessed, and who will have access to the specimens.*

7.2 *List the data to be stored or associated with each specimen.*

7.3 *Describe the procedures to release data or specimens, including: the process to request a release, approvals required for release, who can obtain data or specimens, and the data to be provided with specimens.*

8.0 Sharing of Results with Subjects*

8.1 Describe whether results (study results or individual subject results, such as results of investigational diagnostic tests, genetic tests, or incidental findings) will be shared with subjects or others (e.g., the subject's primary care physicians) and if so, describe how the results will be shared.

Individual subject results will not be shared with subjects or others. Study results in aggregated forms may be published in peer-reviewed

journals or presented at professional conferences or academic talks. The publications may be shared with subjects upon request.

9.0 Study Timelines*

9.1 Describe:

- **The duration of an individual subject's participation in the study.**
 - An individual subject's participation includes up to three assessment visits (pre-intervention visit, post-intervention visit, and follow-up visit) as well as the intervention training. The assessment visits last approximately 60 minutes per visit. The intervention training will last a minimal of 15 minutes. Since part of the purpose of the study is to explore the dose effect of the intervention, we do not set an upper limit of the intervention length, which could depend on patient's preference and patient's length of stay (if inpatient). We expect the total duration of subject's participation to last up to six months (depending on how far out the subject's follow-up appointment is scheduled upon completion of intervention).
- **The duration anticipated to enroll all study subjects.**
 - Approximately 24 months
- **The estimated date for the investigators to complete this study (complete primary analyses)**
 - August 31, 2021

10.0 Inclusion and Exclusion Criteria*

10.1 Describe how individuals will be screened for eligibility.

Using electronic medical records and working with medical colleagues located in the hospital, trained research staff will identify potential participants admitted to NCH with a complicated mild, moderate, or severe TBI. Once identified as eligible to participate, research staff will approach legal guardians and eligible children on the hospital unit to introduce the research project. Staff will ensure children are awake, alert, and able to sign the assent form (if ≥ 9 years) and demonstrate understanding of the study before being approached for consent. In addition, a trauma registry request will be performed monthly to identify TBI patients discharged within the last 3 months. These patients, if eligible, will be mailed a study invitation, followed by an introduction phone call. Additional recruitment of discharged patients will be performed at follow up appointments using study flyers. Patients may also self-refer from the public domain through postings on sites such as clinicaltrials.gov (NCT03611062) and via IRB approved recruitment emails. Discharged patients will be offered the opportunity to

return to the hospital to receive the training. Consent and assent will be obtained at an in-person meeting. All TBI patients will be tracked using a Patient Reminder List in Epic.

10.2 Describe the criteria that define who will be included or excluded in your final study sample.

Inclusion criteria are as follows: 1) diagnosed with TBI (ICD-9 codes 803, 850, 851, or 854) and between 7 to 17 years old (inclusive) when admitted; 2) lowest post-resuscitation Glasgow Coma Scale (GCS)=13-15 combined with trauma-related abnormalities on neuroimaging or a depressed skull fracture (complicated mild TBI, CDC/NIH definition), GCS=9-12 (moderate TBI, CDC/NIH definition), and GCS=3-8 (severe TBI, CDC/NIH definition); 3) fluent in English-based communication; and 4) Physicians note closest to time of enrollment does not include information on agitation; or if under observation for agitation, currently score ≤ 28 on the Agitated Behavior Scale (ABS), indicating mild to no agitation. To minimize the possibility of confounding by comorbidities and cognition, the following exclusion criteria are set, as consistent with existing literature: 1) severe physical/visual/cognitive comorbidities secondary to TBI that prevent proper utilization of a VR-based game and valid administration of the study measures; 2) premorbid neurological disorder or neurodevelopmental issues prior to injury that prevent proper utilization of a VR-based game and valid administration of the study measures; and 3) patients who are restricted from using electronic gaming devices.

10.3 Indicate specifically whether you will include or exclude each of the following special populations: (You may not include members of the above populations as subjects in your research unless you indicate this in your inclusion criteria.)

- **Adults unable to consent:** No
- **Individuals who are not yet adults (infants, children, teenagers):** Yes, this study will include children and adolescents 7-17 years old
- **Pregnant women:** No
- **Prisoners:** No

11.0 Vulnerable Populations*

11.1 If the research involves individuals who are vulnerable to coercion or undue influence, describe additional safeguards included to protect their rights and welfare.

Using electronic medical records and working with medical colleagues located in the hospital, trained research staff will identify potential participants admitted to NCH with a complicated mild, moderate, or severe TBI. Once identified as eligible to participate, research staff will approach legal guardians and eligible children on

PROTOCOL TITLE: Virtual Reality-based Rehabilitation for Children with Traumatic Brain Injuries

the hospital unit to introduce the research project. Staff will ensure children are awake, alert, and able to sign the assent form (if ≥ 9 years) and demonstrate understanding of the study before being approached for consent.

In addition, a trauma registry request will be performed monthly to identify TBI patients discharged within the last 3 months. These patients, if eligible, will be mailed a study invitation, followed by an introduction phone call. Additional recruitment of discharged patients will be performed at follow up appointments using study flyers. Patients may also self-refer from the public domain through postings on sites such as clinicaltrials.gov (NCT03611062) and through IRB approved recruitment emails. Discharged patients will be offered the opportunity to return to the hospital to receive the training.

Consent and assent will be obtained at an in-person meeting. Children will only be approached if the subject is interested in learning more about this research after initial study introduction. The researchers will ensure that the subjects understand that participation is voluntary and will not affect any treatment he/she may receive in the current or future visits.

Link information between study data and patient identification information will be kept separately from the study data and stored on a secure server in a password protected file on a password protected computer located in the Research Institute at Nationwide Children's Hospital at NCH.

12.0 Local Number of Subjects

12.1 Indicate the total number of subjects to be accrued locally.

The study will recruit approximately 30 children with complicated mild, moderate, or severe TBI at Nationwide Children's Hospital.

13.0 Recruitment Methods

13.1 Describe when, where, and how potential subjects will be recruited.

From August 2018 to August 2020, researchers from NCH Center for Injury Research and Policy will work with colleagues throughout various departments/units across the hospital (Inpatient Rehab Unit, Neurosurgery Inpatient Unit, etc.) to identify and approach potential participants admitted to NCH. Other potential participants already discharged will be identified through trauma registry data and mailed invitation letters followed by an introduction phone call. Additional recruitment of discharged patients will be performed at follow up appointments using study flyers. Patients may also self-refer from the

PROTOCOL TITLE: Virtual Reality-based Rehabilitation for Children with Traumatic Brain Injuries

public domain through postings on sites such as clinicaltrials.gov (NCT03611062) and through IRB approved recruitment emails. These participants will also be sent the study letter and receive an introduction phone call if they are interested. Once participants have been identified as appropriate for the VR intervention, the research associates will explain and consent the legal guardian and assent the patient if they are 9 or older.

Subjects will only be approached if the subject is interested in learning more about this research. The researchers will ensure that the subjects understand that participation is voluntary and will not affect any treatment he/she (or their child) may receive in the current or future visits. The legal guardian will give consent for this research, and his/her child will give assent if age ≥ 9 years.

13.2 Describe the source of subjects.

All inpatient and outpatient departments/units at NCH with patients with TBI, including but not limited to Inpatient Rehab Unit, Neurosurgery Inpatient Unit, Outpatient Rehab Unit, Neurosurgery Outpatient Unit. Patients may also be identified through trauma registry data. Participants may also self-refer from the public domain through postings on sites such as clinicaltrials.gov (NCT03611062) and through IRB approved recruitment emails.

13.3 Describe the methods that will be used to identify potential subjects.

Researchers from NCH Center for Injury Research and Policy will work with colleagues throughout various departments/units across the hospital (Inpatient Rehab Unit, Neurosurgery Inpatient Unit, etc.) to identify and approach potential participants admitted to NCH. Other potential participants already discharged will be identified through trauma registry data and mailed invitation letters followed by an introduction phone call. Additional recruitment of discharged patients will be performed at follow up appointments using study flyers. Patients may also self-refer from the public domain through postings on sites such as clinicaltrials.gov (NCT03611062) and through IRB approved recruitment emails.

13.4 Describe materials that will be used to recruit subjects.

Flyers and introductory letters will be used to recruit participants. (attached). Phone, SMS, and email reminders will also be sent prior to the scheduled appointments.

13.5 Describe the amount and timing of any payments to subjects.

Children will be paid \$30 for completing Visit 1 (pre-intervention assessment), \$40 for completing intervention/training and Visit 2 (post-intervention assessment), and \$50 for completing Visit 3 (follow-up assessment). Parents will be paid \$50 for completing Visit

PROTOCOL TITLE: Virtual Reality-based Rehabilitation for Children with Traumatic Brain Injuries

3 (follow-up assessment). All incentives will be paid through Greenphire ClinCards.

Patients who come to the hospital solely for research purposes will also be provided a parking pass free of charge.

Patients/parents will sign receipts for both receiving the ClinCard and the parking pass (if applicable).

14.0 Withdrawal of Subjects*

The research is expected to pose minimal safety/toxicity concerns to subjects. If a subject verbally or behaviorally indicated motion sickness, VR side effects, or other discomfort, he/she will be provided with the option to withdrawn from the study upon request. Medical care will be provided at the direction of the attending physicians/nurses.

If more than 20% of subjects report SAEs due to the study procedures, the researchers will stop the study protocol, re-evaluate and revise the protocol, re-submit it for IRB approval, before resuming participant recruitment

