6.0 Procedures Involved*

The procedure involved for the study is described in detail below:

1) Baseline assessment. All approximately 30 children will complete the NIH Toolbox Cognition Battery tests, CPT 3, Virtual Reality Assessment, and the TBI-QOL Short Form prior to the randomization sequence. Both the assessor and the child will be unaware of group assignment at this point. Additionally, data regarding baseline measurement including proportion of planned baseline measures that are completed and the duration of each assessment will be documented.

2) Intervention. Following the baseline assessment, the approximately 30 children will be randomly assigned to one of the following two groups: intervention group (VICT training) or control group (a comparable VR game without cognitive training). The random allocation sequence will be generated using a SAS-based randomization program with 1:1 allocation ratio and random block sizes of 2 and 4. Both groups will first be provided a tutorial to be familiar with the VR environment. The length of time for either intervention game will be a minimum of 15 minutes of total play. If they are in the hospital, they will play approximately 15 minutes per day during their stay. If they have already been discharged from the hospital, the length of time is a minimum of 15 minutes of total play but can be more spread across their choice of days. Trained researchers who generate the randomization sequence and implement the VR will not participate in any subsequent outcome assessment. Note that although the length of training will vary across children depending on their length of stay or if they have been discharged, this arrangement has unique advantages over a fixed length of training in that: a) it provides consistency with standard therapies children are scheduled to receive, ensuring intervention to meet children's medical needs; and b) it ensures consistent timing and sufficient retention rates for future assessment.

Additionally, AEs and SAEs will be monitored in real-time throughout the intervention. Quantitative user feedback such as sickness, fatigue, and time estimates will be measured at the end of both the first and the last VR session. The

PROTOCOL TITLE: Virtual Reality-based Rehabilitation for Children with Traumatic Brain Injuries

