semi-structured interview from the User Feedback Survey will also be conducted at the first and last VR session on children's perceived VR experience, benefits, and challenges.

3) Post-intervention assessment. At completion of intervention, all children will again complete the NIH toolbox Cognition Battery tests, the Conners CPT 3, the Virtual Reality Assessment, and the TBI-QOL Short Form with trained staff blinded to the intervention assignment. Data regarding post-intervention measurement including proportion of planned post-intervention measures that are completed and duration of each assessment will also be documented.

4) Follow-up assessment. All children will complete a follow-up assessment within approximately 6 months after intervention completion. Clinically, this gives the child and family a long enough time to identify cognitive and behavioral problems. Research staff blinded to group assignment will administer the NIH Toolbox tests, the Conners CPT 3, the Virtual Reality Assessment, and the TBI-QOL Short Form to children at this visit. Children will complete the child-PedsQL Generic Core Scales and their parents or legal guardians/representatives will complete the BRIEF2, CBCL-APS, and parent-PedsQL. Data regarding follow-up measurement including proportion of planned follow-up measures that are completed and duration of each assessment will be documented. Data regarding recruitment including number of children screened per month; number of children enrolled per month; proportion of eligible children who enroll, and treatment-specific retention rates will be documented throughout the study and aggregated at this stage.

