15.0 Risks to Subjects*

We believe that there is minimal risk for being in this study.

It is possible that the subject might feel motion sickness using the virtual reality goggle. They might also experience other virtual reality side effects, which can include but are not limited to, blurry vision, eye strain, headaches, dizziness, fatigue, or nausea. The subject has the right to terminate using the virtual reality goggle any time during the study if there is any discomfort arising from using the virtual reality goggle. The risk of motion sickness will be minimized by allowing subjects to terminate use of the VR intervention at any time during the study.

Although we will take every precaution including secure data storage on password-protected computers and REDCap, there is a small chance of loss of confidentiality of study information. The risks related to patient confidentiality will be minimized by creating a separate link file for patient study ID and the MRN. The study ID will be used on the questionnaires. Patients' medical data will be reviewed and abstracted by trained researchers. All data will be stored on a secure server at NCH. The Patient ID-Participant ID link file will be stored in a separate location on the server from other study data for an additional layer of security and confidentiality.

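### Section 13.5 ties the $40 Visit 2 payment to completing training, which works against the right to stop VR; pay it for attending Visit 2 (minor)

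*Combined protocol and SAP*

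**What the plan says.** Five parts of the combined protocol and SAP bear on the child who stops VR early because of symptoms.

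- **Payment (13.5).** The child receives $30 for Visit 1. The $40 that follows is a single item, "for completing intervention/training and Visit 2 (post-intervention assessment", with no separate or pro-rated amount for the visit. The last $50 for the child is worded "for completing Visit 3 (follow-up assessment). Parents will be paid" a further $50, so neither Visit 3 payment depends on training.
- **Right to stop (15).** "The subject has the right to terminate using the virtual reality goggle any time during the study" if there is discomfort. The same section names stopping as the way the motion-sickness risk is kept down.
- **Withdrawal (14).** For a child who shows motion sickness or other VR discomfort, "he/she will be provided with the option to withdrawn from the study upon request", and medical care is given. Stopping VR while staying in the study is not mentioned here.
- **Dose (6, 9.1).** "The length of time for either intervention game will be a minimum of 15 minutes of total play". Section 9.1 sets no upper limit. Inpatients play on successive days, and discharged children may spread play over days that they choose.
- **Visits (6).** "At completion of intervention, all children will again complete the NIH toolbox Cognition Battery tests", and "All children will complete a follow-up assessment within approximately 6 months after intervention completion". Both visits are planned for all children, and both are dated from the end of the intervention.

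**The concern.** The safeguard in Section 15 and the payment rule in Section 13.5 pull in opposite directions for one kind of child: one who has symptoms, wants to stop for good, and has not yet reached 15 minutes of total play. The safeguard says the child may stop. The payment rule, read as written, makes stopping cost $40, whether or not the child comes to Visit 2. The participants are aged 7 to 17 with a brain injury, and the listed VR effects include headache, dizziness and nausea, so a payment reason to continue is unwelcome even if few children meet it.

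The same rule removes the payment for attending Visit 2, an assessment visit of about 60 minutes. Retention by arm is an Aim 1 measure in Section 17.1, and the trial wants Visit 2 data on every randomized child. For this child the visit also has no clear date, because the event that triggers it, completing the intervention, has not clearly happened.

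**Working it through.** The plan gives no power, alpha or effect-size figure that bears on this point, so there is no figure of its own to reproduce. The check is payment arithmetic, a comparison of sections, and the cost of losing one child.

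**1. Payments.** Inputs from 13.5: child $30, $40 and $50; parent $50 at Visit 3.

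- Child total: 30 + 40 + 50 = $120. Family total: 120 + 50 = $170.
- The $40 as a share: 40/120 = 33% of child payments; 40/170 = 24% of family payments.
- Visit 3 as a share: (50 + 50)/170 = 59% of family payments, not conditional on training.

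**2. What each choice pays the child with symptoms and under 15 minutes of play.** This takes 13.5 literally and takes the 15-minute minimum as the test of completed training.

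| Choice | As worded | If the $40 is for attending Visit 2 |
|---|---|---|
| Plays on to 15 minutes, attends Visits 2 and 3 | 30 + 40 + 50 = $120 | $120 |
| Stops, attends Visits 2 and 3 | 30 + 0 + 50 = $80 | 30 + 40 + 50 = $120 |
| Stops, skips Visit 2, attends Visit 3 | 30 + 0 + 50 = $80 | $80 |
| Withdraws after Visit 1 | $30 | $30 |

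As worded, playing on is worth $40 over stopping (120 − 80), and attending Visit 2 after stopping is worth $0 (80 − 80). With the change, playing on is worth $0 and attending Visit 2 is worth $40.

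**3. Who is affected.** One session lasts about 15 minutes (5.1), so the case arises mainly when symptoms come in the first session. The minimum is cumulative, however, and play may resume on another day. Only a child who stops permanently below the minimum is affected. A child who stops after 15 minutes has arguably completed training and has an ordinary date for Visit 2. The document gives no rate from which to estimate the number of early stoppers.

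**4. Cost of losing one such child.** Inputs: about 30 children, 1:1, so about 15 per arm.

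- Retention: 1/15 = 6.7 percentage points in that arm; 1/30 = 3.3 points overall.
- Unadjusted standard error of the difference, in SD units: √(1/15 + 1/15) = 0.365; with one child lost, √(1/15 + 1/14) = 0.372. The ratio is 1.018, a rise of 1.8%.
- Dose regression (17.1): if the child is in the VICT arm, one point between 0 and 0.25 hours is lost. About 15 controls already sit at dose 0, so that end of the line is well supplied.

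**The case against.** Much of the protection is already in the plan. Section 15 gives the right to stop VR, and Section 14, which is about withdrawal, offers withdrawal only as an option on request. Section 6 keeps all children in for both later visits. Section 17.1 reports adherence separately from retention, so it foresees a child who does not adhere but is retained. All of this stands. A reader of Section 14 alone might infer that a child with symptoms must leave the study; the document does not say so, and the missing cross-reference is mostly a matter of wording.

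It is also fair to say that forfeiture is not stated. Section 13.5 does not define completing training, and the consent form, which would carry the terms put to families, is not in the public document. This stands in part. The plain wording makes the $40 conditional on both elements, but whether staff would withhold it is an assumption.

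Finally, paying for Visit 2 may not raise the protocol completion rate in Section 4.1, because a child below the training minimum may still count as a non-completer. Stopping for symptoms is itself a genuine feasibility signal. That stands too, so the gain to claim is in retention and participant protection, not in the completion rate.

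**Conclusion.** The point holds in a narrow form and is minor. On its wording, Section 13.5 puts $40 of $120 at risk for a child who permanently stops VR for symptoms before 15 cumulative minutes, even if that child attends Visit 2, and Section 6 gives that child no clear date for the visit. This rests on two assumptions: that completing training means reaching the 15-minute minimum, and that the payment rule is applied literally. The number of children affected is unknown and probably small.

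Three stronger inferences are not supported:

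- **Bias between the arms.** The comparator is also a VR game: "control group (a comparable VR game without cognitive training". The same symptoms, payment rule and visit rule apply in both arms, and nothing in the document suggests that early stopping would differ between them.
- **Material damage to the analyses.** A rise of 1.8% in the standard error per child lost, or the loss of one low-dose point, changes little in an exploratory study that states no hypotheses to be tested.
- **Lost safety data.** Adverse events are monitored in real time during the intervention (Section 6), so the event that led the child to stop is still counted.

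**What to change.** Three short wording changes:

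1. **Section 13.5:** pay the $40 for attending Visit 2, whether or not the training minimum was reached.
2. **Section 6:** for a child who stops VR permanently before the minimum, time Visits 2 and 3 from the last VR session.
3. **Section 14:** cross-refer to Section 15 and state that stopping VR is not withdrawal from the study. Keep the right to withdraw fully as it is. Recording the reason for stopping would be a useful addition.

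The cost is a short amendment and a few extra $40 payments. With about 30 children this item cannot exceed 30 × $40 = $1,200, the amount due in any case if every child completed training and attended. No new staff or procedures are needed. In return, the payment reason to play through symptoms goes, and a child who stops early has a paid and dated Visit 2.

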16.0 Potential Benefits to Subjects*

There are no known direct physical, psychological or social benefits immediately for the subject, although it is possible that the subject might have fun playing the virtual reality games and he/she might experience improved cognitive rehabilitation with use of the virtual reality tools.

In general, we anticipate that this study will provide critical data to improve rehabilitation methods available for pediatric TBI patients, and potentially help future patients to further improve TBI rehabilitation.

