18.0 Provisions to Monitor the Data to Ensure the Safety of Subjects*

Not Applicable as the study involves no more than minimal risk to subjects.

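### The only study-level safety hold, more than 20% of subjects with procedure-related SAEs, has no defined denominator and is lenient for a minimal-risk study in children

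*Combined protocol and SAP*

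**What the plan says.** Section 14.0 sets one rule for the study as a whole: "If more than 20% of subjects report SAEs due to the study procedures, the researchers will stop the study protocol". The researchers must then revise the protocol and "re-submit it for IRB approval, before resuming participant recruitment". The section does not say whether the denominator is children exposed so far, children enrolled so far or the planned total, which sections 1.0 and 12.1 put at approximately 30. It gives no minimum count and no timing for the check.

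No other study-level hold appears:
- Section 6.0 states that "AEs and SAEs will be monitored in real-time throughout the intervention" but attaches no action threshold.
- Section 18.0, on monitoring data for safety, reads "Not Applicable as the study involves no more than minimal risk to subjects".
- The other provisions in sections 14.0 and 15.0 concern the individual child, who may stop VR or withdraw.

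The stated premise is low risk: "The research is expected to pose minimal safety/toxicity concerns to subjects" (section 14.0) and "We believe that there is minimal risk for being in this study" (section 15.0). Section 16.0 says "There are no known direct physical, psychological or social benefits immediately for the subject". Both arms use VR, since controls receive "a comparable VR game without cognitive training".

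**The concern.** The threshold and the premise do not fit together. In a minimal-risk study with no known direct benefit, a second child with an SAE caused by the VR procedures is a good reason to stop and look again. The written rule usually does not require it.

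The missing denominator is a separate defect. Two people applying the rule in good faith could reach different decisions on the same events. At an assumed 10% risk per child, the chance that the rule ever fires is 44% on one reading and 2.6% on the other.

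What is at stake is child protection. No endpoint or efficacy analysis is affected.

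**Working it through.** The plan states no operating characteristics for this rule, so there is no figure to reproduce.

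**Inputs.** Threshold: strictly more than 20% (section 14.0). Sample size: n = 30 (sections 1.0 and 12.1, approximate). Both arms are pooled, because the rule speaks of subjects and both arms use VR.

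**Running reading (children exposed to date).** The rule fires at the first point where affected/exposed > 0.20.
- First affected child: 1/4 = 25% fires and 1/5 = 20% does not, so it fires only at position 4 or earlier.
- Second affected child: 2/9 = 22.2% fires and 2/10 = 20% does not, so it fires only at position 9 or earlier.
- With two affected among 30, no pause needs the first at position 5 or later and the second at position 10 or later: C(26,2) − C(5,2) = 325 − 10 = 315 of C(30,2) = 435, or 72.4%.

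For k affected children the no-pause share is (n − 5k + 1)/(n − k + 1):

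| k | Share with no mandated pause |
|---|---|
| 2 | 21/29 = 72% |
| 3 | 16/28 = 57% |
| 4 | 11/27 = 41% |
| 5 | 6/26 = 23% |
| 6 | 1/25 = 4% |

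**Fixed reading (denominator 30).** 6/30 = 20.0% does not fire and 7/30 = 23.3% does. With two to six affected children there is never a mandated pause.

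**Sensitivity of the 72%.** With 28 to 32 children it is 70.4% to 74.2%. Reading the rule as 20% or more gives 66.7%. If one to three further children are already exposed when an SAE is counted, it is 78% to 91%.

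**With assumed SAE risks.** The documents give no rate, so each per-child risk p below is an assumption. The amended rule (see the fix) uses the running denominator, so the 20% clause still fires at a related SAE in any of the first four children, and the added clause fires at the second affected child. Its chance of a first pause is 1 − (1−p)^4 × [(1−p)^26 + 26p(1−p)^25]. At p = 0.01 this is 1 − 0.9606 × (0.7700 + 0.2022) = 0.066.

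| | p = 1% | 5% | 10% | 20% |
|---|---|---|---|---|
| First pause, running | 0.040 | 0.210 | 0.438 | 0.821 |
| First pause, fixed | 0.000 | 0.001 | 0.026 | 0.393 |
| First pause, amended | 0.066 | 0.492 | 0.835 | 0.991 |
| Two or more affected, no pause, running | 0.026 | 0.281 | 0.397 | 0.170 |
| Two or more affected, no pause, fixed | 0.036 | 0.446 | 0.790 | 0.596 |

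Against the running reading, every added first pause falls in a trial with at least two affected children (at 1%, 0.066 − 0.040 = 0.026).

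**Expected gain.** Treat the first pause as ending exposure for good, which favours the change. SAEs averted = p × difference in expected children exposed.
- p = 1%: running 0.01 × (28.89 − 28.69) = 0.002; fixed 0.01 × (30.00 − 28.69) = 0.013.
- p = 5%: running 0.05 × (24.39 − 21.83) = 0.13; fixed 0.05 × (30.00 − 21.83) = 0.41.
- p = 10%: running 0.10 × (18.79 − 14.49) = 0.43; fixed 0.10 × (29.90 − 14.49) = 1.54.

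**The case against.** **The benefit is negligible if the premise is right.** Section 15.0 names effects such as motion sickness, eye strain, headache and nausea, which are not serious as listed. At 1% the change buys 0.002 averted SAEs for 0.026 extra first pauses, about 13 protocol revisions and IRB re-submissions per SAE averted on the running reading, or about 5 on the fixed one (0.066/0.013). This stands and keeps the point minor.

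**Two is a preference.** Nothing in the documents picks two over one or three. This also stands: the count is a judgement about what minimal risk can tolerate.

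**Some protection exists already.** SAEs are watched in real time, a child can stop at any moment, and nothing prevents an earlier voluntary pause. This is true, but none of it is a study-level rule. A sponsor that writes such a rule should make it usable.

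**A count alone might seem enough.** A reader might infer that the 20% clause should be replaced by a pause at the second affected child. That would leave no trigger after recruitment resumes, which section 14.0 expects. With SAEs at children 12, 13 and 14, a bare count pauses at 13 and then mandates nothing, whereas the running 20% rule fires at 3/14 = 21.4%. The count must be added to the clause.

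**Conclusion.** The concern holds as a minor, cheap improvement. Section 14.0 leaves its denominator undefined, and on either reading more than 20% is lenient for this study. With two affected children among 30, no pause is mandated in 72% of orderings (running) or in all of them (fixed).

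The 72% rests on exposure one child at a time, equally likely orderings, and a check after every child with each SAE counted at that child's exposure. The documents specify none of these. Overlapping exposure or late counting would raise it.

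Two stronger inferences are not supported. A reader might take 72% as the chance that the trial overlooks harm. It is conditional on two related SAEs having occurred; at an assumed 1% risk, two or more affected children with no mandated pause arises in 2.6% of trials (running) or 3.6% (fixed). A reader might also infer that the rule is ineffective throughout. On the running reading it pauses in 82% of trials at an assumed 20% risk, and six affected children go unpaused in only 4% of orderings.

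**What to change.** In section 14.0 keep the 20% clause and state that its denominator is all children with at least one VR session to date, both arms combined, assessed at each procedure-related SAE. Then add: *Recruitment and VR sessions also pause when a second exposed child has a procedure-related SAE and, after any resumption, at each further child with one.* Keep the existing re-evaluation and IRB re-submission. In section 18.0 replace the not-applicable entry with a reference to this rule and to the real-time monitoring in section 6.0.

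The cost is a few lines of text, with no extra patients, visits or data. The operational price is an occasional extra pause with IRB re-submission, within an enrolment period that section 9.0 puts at about 24 months. At an assumed 1% risk the chance of a first pause rises from 4.0% to 6.6% on the running reading, or from about 0% to 6.6% on the fixed one.
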